Safety profile of resveratrol in clinical studies

The dose and preparation of resveratrol in clinical trials varies widely (from 5 mg to 5 g daily) but consistently displays a reassuring safety profile and tolerability profile. Doses up to 5 g daily in healthy volunteers were safe and well-tolerated, with mild adverse effects (gastrointestinal disturbance, headache and myalgia and no severe adverse effects or laboratory abnormalities).^{71,72} Minor elevation of bilirubin was seen in an eight week study in liver disease at 3g daily.⁷³

Body mass index fell after resveratrol treatment in one study.⁷⁴ This may be relevant in bronchiectasis, where a BMI <18.5kg/m² is linked to worse outcomes.¹⁰

Pharmacokinetic profile of resveratrol

Oral bioavailability of resveratrol is low, but wide inter-individual variability exists.⁷⁵ It undergoes rapid metabolism to 3 main metabolites (resveratrol-3-O-sulphate, resveratrol-4'-O-glucuronide and resveratrol-3-O-glucuronide).^{72,76} Serum metabolite concentrations exceed concentrations of free resveratrol; these metabolites have similar antioxidant effects and may contribute to the activity of resveratrol, with synergistic effects observed.^{60,77-79} Assessment of total resveratrol levels (i.e. measuring levels of resveratrol *and* metabolites) is therefore important. Time to maximum resveratrol concentration is 0.8-1.3 hours, and 2.8-3.2 hours for metabolites. Half-life for resveratrol is 5.1 hours and 7.8-8.4 hours for metabolites.^{80,81}

Another important consideration is back-conversion of the glucuronated and sulphated metabolites to resveratrol: therefore, the metabolites act as a "reservoir" for resveratrol.^{82,83} Resveratrol has been shown to accumulate in tissues (e.g. liver, skeletal muscle), with much higher tissue resveratrol concentrations than in serum; tissue levels of resveratrol may exceed tissue levels of its metabolites.^{68,76,82}

Therefore, despite initial low bioavailability, resveratrol and its metabolites may act together to exert localised tissue effects. Sputum levels of resveratrol have not been assessed previously and will be part of this study.

Sputum neutrophil elastase in bronchiectasis

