Secondary aims: To assess whether resveratrol has antimicrobial and antioxidant activity in adults with bronchiectasis; to determine the optimal dose of resveratrol in terms of anti-inflammatory, antimicrobial, and antioxidant effects, bioavailability, adherence, tolerability and safety in adults with bronchiectasis.

Study design

Single centre, single-arm, pre-post, open-label study in patients with stable bronchiectasis over 12 weeks. The study will incorporate a sub-study, whereby participants will be randomised to receive either 500 mg twice daily, or 1000 mg twice daily

Study centre and recruitment

The study site is Middlemore Hospital, South Auckland. The hospital serves a population of approximately 510,000 people with relatively large Māori (16%) and Pacific (23%) populations. Patients will be identified using a departmental research database of patients with bronchiectasis, and using clinical coding data (ICD-10) for patients attending outpatient clinics and discharged from hospital with a diagnosis of bronchiectasis.

We plan to recruit 40 patients for this study.

Inclusion criteria

- Aged ≥ 18 years
- Able to provide written informed consent
- Able to provide spontaneous sputum sample at visit 2 (week 0)
- High-resolution CT (HRCT) chest scan confirming diagnosis of bronchiectasis within 5 years
- Clinically stable during baseline period, for 4 weeks prior to commencement of treatment (defined as the absence of clinical worsening beyond normal daily variation, with no need for increasing habitual medications or taking antibiotics or prednisone, with stable spirometry)
- History of one or more pulmonary exacerbations requiring antibiotics in the past 12 months.
- Patients with asthma and COPD will be included if the primary diagnosis is bronchiectasis

Exclusion criteria:

- Patient using current oral, intravenous or inhaled antibiotics within 4 weeks prior to commencing study drug
- Patients taking continuous macrolide therapy (≥ 3 months) within 3 months of screening
- Patients taking continuous oral corticosteroids (>6 weeks)
- Bronchiectasis exacerbation or respiratory infection requiring oral or intravenous antibiotic treatment within 4 weeks prior to commencing study treatment
- Use of prescribed or dietary antioxidant supplement within 1 month of screening
- Body mass index <18.5 kg/m²
- Patients with a history of non-compliance with medications
- Patients with significant medical conditions other than bronchiectasis:

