Substance:	Resveratrol 500 mg + piperine 5 mg + polydatin 5 mg (“Transmax”)
Form:	Capsule
Unit strength:	500 mg
Route of administration:	Oral

Dosage regimen

Oral resveratrol will be commenced at a dose of either 500 mg twice daily or 1000 mg twice daily.

Treatment will continue at this dose for the duration of the study (12 weeks). Patients will be advised to take the study product with food to maximize absorption.^{79,95}

Test drug dispensing

Participants will be issued with resveratrol at visits 2 (week 0) and 3 (week 4). 40 participants will each receive a blister pack supply of 500 mg capsules for 4 weeks at visit 2, and for a further 8 weeks at visit 3, according to the dosage regime to which they are allocated.

Participants will be advised to contact the research team if adverse effects develop. If adverse effects are experienced, patients can opt to *reduce by one dose step* after consultation at either a clinic visit or following telephone communication. Dose steps will be 2000 mg a day, 1000 mg a day and 500 mg a day.

Adherence will be monitored and measured by keeping a record of the number of tablets issued and returned. Patient's adherence with the proper use of the study drug will be assessed at visits 3 and 4, and patients will be reminded to bring all study medication pack(s) (used or unused) and completed diaries to these visits.

Packaging and labelling

Biotivia LLC, New York, USA will provide the capsules containing 500 mg resveratrol. The following will be printed on each compliance pack: trial number, medication number, packet number, participant initials, directions for use, expiry date, caution statement, storage instructions, space for "date dispensed", and name and address of host institution. All used trial medication packs are to be returned to the patient treatment box for drug accountability.

Concomitant Medications

Any medication that patients take other than the study drug, including herbal medicine or supplement, is considered as concomitant medication and must be recorded in the worksheets.

At screening (visit 1), patients will be asked about all medications they have taken during the last 12 months with special attention to the use of antibiotics, corticosteroids, antioxidant and dietary supplements, and bronchodilators. These should be reviewed at every subsequent study visit.

Safety Parameters

Adverse events

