An adverse event (AE) is defined as any untoward medical occurrence, including an exacerbation of an existing condition in a trial participant receiving a pharmaceutical product. The event does not necessarily have to have a causal relationship with this treatment.

A serious adverse event is defined as any AE which results in death, is immediately life threatening, results in persistent or significant disability, requires or prolongs participant hospitalisation, is a congenital anomaly or birth defect, or is an important medical event that may jeopardise the patient or require intervention to prevent one of the above outcomes.

It is the responsibility of the investigator to record and report all AEs (both serious and non-serious) occurring during the course of the clinical trial (from signing the informed consent form through to the end of the trial). It will be derived by spontaneous, unsolicited reports of patient, by observation and by routine open questionings such as "Has there been any change in your health since I last saw you".

All adverse events will be fully documented on the worksheet with the onset, intensity, seriousness, outcome and action taken, including change in dosage of study drug.

All serious adverse events and unexpected serious adverse reactions (SUSARs) will be reported to the study Data Monitoring Committee. The Health and Disability Ethics Committee (HDEC) do not require notification of SAEs and SUSARs but *urgent safety measures* (to protect participants from a serious, immediate hazard to their health and safety) will be notified to the HDEC within 7 days.

Clinical trial participants alert card

Participants will also be issued with a clinical trial participant's alert card containing information of the study and contact phone numbers of the study staff, to carry throughout the duration of the study.

Study Procedures

There will be 4 visits (screening [visit 1]; treatment commencement [visit 2]; 4 weeks [visit 3]; and 12 weeks [visit 4]).

There will be a 2-4 week baseline period between screening (visit 1) and commencing treatment (visit 2). At visit 2, patients will be randomised to receive either 500 mg twice daily, or 1000 mg twice daily. Participants will be randomized in a ratio of 1:1, with 20 participants in each group of the sub-study. Randomisation will be performed with the use of a computer-generated sequence with random block sizes of 2 and 4.

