Participants have to be clinically stable for at least 4 weeks with no event-based exacerbations before commencing treatment to ensure clinical stability.

Clinical assessment (visits 1, 2, 3, 4)

This will include documentation of subject characteristics, medications, and measurement of vital signs (pulse, blood pressure, and temperature at every visit. Physical examination (general, cardiovascular, respiratory, abdominal examinations) will be done by an investigator at all study visits.

Simple blood tests (visits 1 and 4)

Blood samples will be taken to measure full blood count (FBC), urea & electrolytes (U&E), liver function tests (LFT) and highly-sensitive C-reactive peptide (hs-CRP) at visits 1 and 4. For female participants of child-bearing potential, a serum β -hCG level (pregnancy test) will be measured at screening (visit 1). A urinary pregnancy test will be done at visit 2 prior to commencement of study medication and again at visit 4.

Sputum analysis

Participants will be asked to provide a baseline spontaneous sputum sample at visit 2. Participants who are productive of only a small volume of sputum or have difficulty expectorating will be asked to provide a baseline sputum sample within one week of visit 2. Samples are also required at visits 3 and 4.

Sputum will be processed using standardised guidelines in keeping with the European Respiratory Society Task Force document regarding sputum induction and processing.^{96,97} Spontaneous sputum specimens (sputum plus saliva) will be obtained at visit 2. If participants are unable to provide a sputum sample at visit 3 or 4, induced sputum samples will be collected (see below); samples will be processed within 2 to 4 hours of collection.

Sputum supernatant for measurement of neutrophil elastase, cytokines, hs-CRP and total antioxidant capacity will be separated and frozen at -70°C for measurement at the completion of the study.

Induction of sputum

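### The one-week allowance for the baseline sputum sample does not require it to precede the first capsule, so some baselines may be on-treatment values

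*Protocol*

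**What the plan says.** **Start of treatment.** Study Procedures labels visit 2 as the start of treatment and adds: "There will be a 2-4 week baseline period between screening (visit 1) and commencing treatment (visit 2"). Test drug dispensing says: "Participants will be issued with resveratrol at visits 2 (week 0) and 3 (week 4").

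**Baseline sputum, main rule.** Sputum analysis says: "Participants will be asked to provide a baseline spontaneous sputum sample at visit 2". Later in that section, spontaneous specimens are again placed at visit 2. The schedule of visits shows no sputum collection before visit 2.

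**Baseline sputum, exception.** Participants who produce only a small volume, or who have difficulty expectorating, "will be asked to provide a baseline sputum sample within one week of visit 2".

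**Eligibility.** One inclusion criterion is: "Able to provide spontaneous sputum sample at visit 2 (week 0").

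**Analysis.** The Analysis plan equates baseline with visit 2. It regresses the change at visit 4 from baseline on the baseline value.

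**Timing relative to first dose.** Where the authors wanted a pre-dose procedure they said so: "A urinary pregnancy test will be done at visit 2 prior to commencement of study medication". The baseline sputum sample carries no such condition. The only dose-timing instruction linked to sampling, under the resveratrol levels, concerns the morning dose on visit days and does not address a late baseline.

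**The concern.** A site following the text can randomise and supply a participant at visit 2, let dosing begin, and accept a sputum sample several days later as baseline. In this uncontrolled pre-post design, the participant's own baseline is the only reference for the primary aim. It also enters the primary analysis twice, as the value subtracted and as the regressor. The same sample supplies the baseline for sputum cytokines, antioxidant capacity and resveratrol level.

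For the resveratrol level the problem is direct. A baseline taken after dosing is not an unexposed level, whatever the drug does to inflammation. For elastase, the loss depends on how much effect is present when the late sample is given. The affected participants would be a selected group, those who produce little sputum. A pre-dose sample that was not taken cannot be recovered at analysis.

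**Working it through.** **1. The text.** Treatment starts at visit 2, the exception allows a sample within a week of visit 2, and no condition ties that sample to the first capsule. A post-dose baseline is therefore permitted, though not stated. The exception also sits uneasily with three other statements: the inclusion criterion, the sentence placing spontaneous specimens at visit 2, and the analysis plan's definition of baseline.

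**2. Exposure.** The protocol reports: "Half-life for resveratrol is 5.1 hours and 7.8-8.4 hours for metabolites". Five of the longest half-lives are 5 × 8.4 = 42 hours, so a sample from about day 2 onwards would be near steady state in serum. This concerns drug level, not effect.

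**3. The plan's power figure.** Sample size gives 40 participants, 10% drop-out (36 completers), a 40% fall (5 to 3 µg/ml) and 80% power. Tests are two-sided at 10%. The log effect is |ln 0.6| = 0.511. The 80% cannot be rerun, because the lognormal parameters and the within-patient correlation are not given. It is attainable: the first cited study (median 15, IQR 3–23) converts to a mean of about (3 + 15 + 23)/3 = 13.7 and an SD of about 20/1.35 = 14.8, hence a log SD of √ln(1 + 14.8²/13.7²) = 0.88. With zero correlation, a normal approximation for the paired change then gives 79% power.

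**4. Calibration.** I solved for the SD of the log change that returns the stated power. With 35 degrees of freedom (critical t = 1.690), a noncentrality of 0.511 × √36 / SD gives 80% power when SD = 1.209. This SD is back-solved, not taken from the protocol.

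**5. Effect of late baselines on a mean log change.** Let f be the share of participants with a post-dose baseline and g the share of the final log effect already present then. Neither is in the documents. The apparent log effect is 0.511 × (1 − f·g). Example: with f = 0.2 and g = 0.5 it is 0.511 × 0.9 = 0.460, so the apparent fall is 1 − e^(−0.460) = 37%, the noncentrality is 0.460 × 6 / 1.209 = 2.28, and power is 72%.

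| Effect already present (g) | f = 10% | f = 20% | f = 30% |
|---|---|---|---|
| none | 40.0% fall, power 80.0% | 40.0%, 80.0% | 40.0%, 80.0% |
| one quarter | 39.2%, 78.2% | 38.4%, 76.3% | 37.7%, 74.4% |
| one half | 38.4%, 76.3% | 36.9%, 72.3% | 35.2%, 68.0% |
| all | 36.9%, 72.3% | 33.5%, 63.5% | 30.1%, 53.9% |

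For one participant with a true fall from 5 to 3 µg/ml, a late baseline with half the log effect present reads 5 × 0.6^0.5 = 3.9 µg/ml. The apparent fall is then 1 − 3/3.9 = 23%.

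**6. The planned regression.** On the log scale, a baseline lowered by k moves that participant's point left by k and up by k. Take a straight-line fit with slope between 0 and −1. If the affected participants lie at the low end of baseline elastase, the slope becomes more negative, which is the direction of the alternative hypothesis. If they lie at the high end, it flattens. The documents do not say where low sputum producers lie, so the direction is not fixed.

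**The case against.** The best defence is that the phrase gives no direction. The sample is called a baseline, a pre-treatment period of 2 to 4 weeks exists, and the analysis ties baseline to visit 2. A careful site might well collect it before dosing. This stands in part: the protocol does not prescribe on-treatment baselines, and a reader who infers that it does goes beyond the text. But no earlier sputum collection is scheduled, and nothing excludes a post-dose sample.

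A reader might also infer a flat contradiction with the inclusion criterion. That is too strong. Producing little sputum, or producing it with difficulty, is not the same as being unable to give a sample. If the criterion is enforced, the exception reaches only people whose visit 2 sample was inadequate, and the share may be small. No figure in the protocol supports 10%, 20% or 30%.

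A third tempting step is from steady-state drug level to full effect on elastase. The protocol gives no onset time for elastase. It says that sputum levels of resveratrol have not been assessed before and that tissue levels differ from serum. The bottom row of the table is therefore an extreme, not an expectation.

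Finally, the power figures are for a mean change, not for the planned regression, so they do not show that the primary analysis loses power or is biased towards no effect. That is correct, and they serve only as a scale. What remains is that the reference value for the primary endpoint is left open on the one point that makes it a baseline.

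**Conclusion.** The point holds as a gap in the definition of baseline: as written, the plan permits post-dose baselines for the primary endpoint and the other sputum measures, and the passages on baseline timing do not fit together. How often this would happen, and how much it would matter for elastase, cannot be learned from the document. On the assumptions shown, the consequence for a mean log change runs from none (80% power) to a serious loss (54% with 30% late baselines and the whole effect present). Half the effect gives about 76%, 72% and 68%. For the planned regression, the result becomes harder to interpret, in a direction that cannot be stated in advance. For the baseline sputum resveratrol level, the damage needs no assumption about the onset of any anti-inflammatory effect. The gap is worth closing before enrolment, because it concerns the only comparator in the design and cannot be repaired afterwards.

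**What to change.** State one rule in Sputum analysis: the baseline sputum sample is collected before the first capsule, either at visit 2 or in the existing pre-treatment baseline period, and within the 2 to 4 hour processing limit. Record the time of the sample and of the first capsule on the worksheet. In the Analysis plan, state that a post-dose sample is not used as baseline in the regression of change on baseline, or else flag it and add a sensitivity analysis without it. Reconcile the inclusion criterion, the sputum section and the analysis plan's definition of baseline with this rule.

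The cost is a sentence or two in each section and two time fields. A few participants may need an extra pre-dose collection, and samples brought from elsewhere must still meet the processing limit. Anyone without a pre-dose sample drops out of the change analysis, and that is not free. Losing 10%, 20% or 30% of the 36 completers leaves about 32, 29 or 25 (36 × 0.9, 0.8, 0.7). By the same calculation, power is then about 76%, 72% or 66%, close to the figures for keeping late baselines with half the effect present. Excluding late samples protects the meaning of the baseline but does not restore power, so the gain lies in obtaining the sample before dosing.

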 - A significant disease is one that would, in the opinion of the investigator, put the participant at risk through participation in the study, or a disease which may influence the results of the study, or the participant's ability to participate in the study.
- Patients with cystic fibrosis
- Patients with primary ciliary dyskinesia
- Patients with hypogammaglobulinaemia

- Patients with allergic bronchopulmonary aspergillosis (defined as the presence of asthma, total serum IgE > 1000 IU/ml, with detectable specific IgE to Aspergillus or positive Aspergillus skin test)
- Patients taking immunosuppressive agents (e.g. azathioprine, methotrexate, cyclophosphamide)
- Patients with other primary or acquired immunodeficiency
- Patients with evidence of active or suspected cancer and patients having undergone cancer treatment including resection, radiation therapy or chemotherapy within the last 2 years (patients with basal cell carcinoma and squamous cell carcinoma are allowed)
- Pregnant or lactating women
- Participation in a separate clinical or device trial within 4 weeks of screening
- Allergy to any of the components of Transmax

Reasons for discontinuation of study medication

- Participant request to discontinue treatment
- Adverse event that contraindicated further dosing, in the opinion of the investigator
- Risk to subject, as judged by the investigator
- Pregnancy
- Discontinuation of the study at the request of the Data Monitoring Committee or regulatory agency, institutional review board or independent ethics committee

Participants who prematurely discontinue treatment should continue in the study until the final visit, if possible. It is highly recommended that all study procedures, including any scheduled visits, are continued until the final visit, if possible.

Withdrawal of participants from the study

- Participant request to withdraw from study
- Lost to follow-up
- Investigators deem that participants are at significant risk of harm from study medication or procedures
- The Data Monitoring Committee requests patient withdrawal due to major safety concerns

Criteria for termination of the study

- Investigators deem that participants are at significant risk of harm from study medication or procedures
- Investigators reserve the right to terminate the study if adequate resources or funding are no longer available to continue the study

Study medication

Investigational products

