Tolerability will be recorded dichotomously and defined as successful completion of the study. Adherence will be described as percentage of capsules taken calculated from prescribed and returned medication. We will record participation consent probability, recruitment and drop-out events.

End points

Primary end point: Change in sputum neutrophil elastase

Secondary end points:

- Sputum hs-CRP
- Sputum cytokines – GM-CSF, IL-1 β , IL-6, IL-8, TNF- α
- Sputum purulence
- Sputum cathelicidin (LL-37)
- Sputum procalcitonin
- Sputum culture
- Sputum and serum total antioxidant capacity
- Sputum and serum resveratrol levels (and metabolites)
- Pulmonary exacerbation frequency
- Lung function (spirometry: FEV1, FVC)
- Health-related quality of life
 - St George’s Respiratory Questionnaire
 - Bronchiectasis Health Questionnaire
 - Leicester Cough Questionnaire
- Adverse events
- Adherence, tolerability and safety of oral resveratrol supplementation
- Requirement for induction of sputum at Visit 4

Statistical Methods

Analysis plan

The analysis will take place in an intention-to-treat analysis set. Our primary aim is addressed by the hypothesis that the primary outcome (*sputum neutrophil elastase levels*) at visit 4 will decline from high values at visit 2 (baseline), or remain stable from low values at visit 2. Accordingly, the primary analysis will consist in a regression of the change at visit 4 from baseline on the value at baseline, using a suitable parametric model, a flexible smooth model for the baseline value and appropriate adjustments (including adjustments for dosage in interaction with baseline).

The alternative hypothesis then translates as a negative relationship between baseline and difference at visit 4. The model is provisionally identified as lognormal, inferred from the literature, but a data review will be effected to confirm.

Safety data will be reported in detail by arm and stratified by severity and causality, using Common Terminology Criteria for Adverse Events (CTCAE) standard. *Tolerability and adherence* will be regressed on the dosage arm using logistic and linear regression respectively. As this is a signal-finding study, tests will be conducted at a significance level of 10% against two-sided alternatives, with no adjustment for multiplicity.

Sample size

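### Tolerability is scored as study completion, so it measures retention and under-counts participants who stop or step down for adverse effects yet attend visit 4

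*Protocol*

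**What the plan says.** The definition stands at the end of Study Procedures, just before End points: "Tolerability will be recorded dichotomously and defined as successful completion of the study". Adherence, defined next to it, is the percentage of capsules taken, worked out from prescribed and returned medication. Under Statistical Methods, Analysis plan, tolerability and adherence "will be regressed on the dosage arm using logistic and linear regression respectively".

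Three other provisions decide who completes:

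- **Stopping the drug is not leaving the study.** Reasons for discontinuation of study medication include "Adverse event that contraindicated further dosing, in the opinion of the investigator". The same section adds: "Participants who prematurely discontinue treatment should continue in the study until the final visit, if possible", and then: "It is highly recommended that all study procedures, including any scheduled visits, are continued until the final visit, if possible".
- **Leaving the study has its own list.** Withdrawal of participants from the study includes "Lost to follow-up" and participant request, which need have nothing to do with the capsules. It also includes withdrawal because the investigators see a significant risk of harm.
- **Step-down is allowed.** Under Test drug dispensing, if adverse effects occur "patients can opt to *reduce by one dose step* after consultation". The steps are given as: "Dose steps will be 2000 mg a day, 1000 mg a day and 500 mg a day".

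The secondary aims name tolerability among the criteria for the optimal dose, and it is listed as a secondary end point.

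**The concern.** A tolerability endpoint in a two-dose comparison should say whether people could stay on the dose they were given. This one says whether they reached the last visit. The retention instruction is good practice for the intention-to-treat analysis, but it works against this definition: the better it is followed, the less intolerance the endpoint records. The step-down option adds to this. A participant allocated 2000 mg a day who steps down for adverse effects goes to the other arm's dose and can still count as a success for 2000 mg a day.

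At stake is one of the criteria on which the two doses are to be compared before a larger trial. When the arms differ in intolerance and the affected participants stay, the comparison is pulled towards no difference. Unrelated losses add noise.

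**Working it through.** The protocol gives no tolerability rate or power for this comparison, so there is no figure to reproduce. The check has three parts.

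**1. How participants are classified**

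| Course | Completes? | Scored as | On the allocated dose at week 12? |
|---|---|---|---|
| Stops in week 1 for an adverse effect, attends visit 4 | yes | tolerated | no |
| 2000 mg a day, steps down for an adverse effect, attends visit 4 | yes | tolerated | no |
| Stops for an adverse effect and leaves the study | no | not tolerated | no |
| Lost to follow-up for an unrelated reason | no | not tolerated | unknown |

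Rows 1, 2 and 4 are the problem. Row 3 is scored correctly.

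**2. How much the comparison is diluted**

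From the protocol: 20 per arm, two-sided 10% level. Assumed, because the protocol gives no values: true intolerance t (stopping or stepping down for adverse effects), the share s of intolerant participants who stay to visit 4, and unrelated loss u, with s and u equal in both arms.

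Observed failure = 1 − (1 − u)(1 − t(1 − s)).
Observed risk difference = (1 − u)(1 − s) × true risk difference.

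With t = 10% and 40% and u = 0:

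| s | Observed failure | Difference (points) | Power, Fisher | Power, normal approximation |
|---|---|---|---|---|
| 0 (same as counting intolerance directly) | 10% v 40% | 30 | 62% | 72% |
| 50% | 5% v 20% | 15 | 21% | 41% |
| 80% | 2% v 8% | 6 | 1% | 22% |
| 90% | 1% v 4% | 3 | 0.1% | 15% |
| 100% | 0% v 0% | 0 | no signal | no signal |

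The normal approximation is unreliable at such small counts. Fisher's test is conservative, but it is the safer guide here. The dilution factor does not depend on the test.

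With u = 10% and s = 80%: 1 − 0.9 × 0.98 = 11.8% and 1 − 0.9 × 0.92 = 17.2%, a difference of 0.9 × 0.2 × 30 = 5.4 points, with Fisher power of 5%.

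Other assumed pairs with u = 0, Fisher power at s = 0, 50% and 80%: for 5% v 30%, 54%, 12% and 0.5%; for 10% v 50%, 84%, 38% and 3%.

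A limiting case: suppose 6 of 20 on 2000 mg a day and 1 of 20 on 1000 mg a day stop or step down for adverse effects, all attend visit 4, and nobody else is lost. The protocol's endpoint reads 100% v 100%. Counting stops and step-downs gives 14/20 = 70% v 19/20 = 95% (Fisher p = 0.091).

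**3. Whether adherence would show a step-down**

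Take a step-down from 2000 to 1000 mg a day at visit 3 (week 4, assumed), with every capsule taken as then advised. Capsules are 500 mg, so 4 a day and then 2 a day. Taken: 28 × 4 + 56 × 2 = 224. Due at the allocated dose: 84 × 4 = 336. Adherence is 224/336 = 67% if the denominator follows the allocated dose, and 224/224 = 100% if it follows the reduced dose. The protocol does not say which.

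**The case against.** The strongest reply is that the endpoint is diluted but not blind, and that it does not stand alone.

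- **A reader might infer that the endpoint cannot detect intolerance at all.** The protocol does not support that. Staying on is requested only if possible, participants may leave, and investigators may withdraw those at risk of harm. Such cases count as failures. The 100% v 100% result needs every affected participant to attend visit 4 and no other losses, whereas the sample-size section assumes 10% drop-out.
- **A reader might infer that a poorly tolerated dose would pass unnoticed into the large trial.** That also goes too far. Safety is reported by arm, severity and causality, the adverse-event worksheet records changes of study drug dosage, and adherence is compared between arms. The optimal dose rests on several criteria together.
- **A reader might infer that a step-down counts as full adherence.** This is not established. Test drug dispensing describes supply according to the allocated regimen and counts of capsules issued and returned, which would show the shortfall. The adherence definition refers to prescribed medication, and that is ambiguous after a step-down.
- **A reader might add that logistic regression will usually fail on empty cells.** At 10% non-completion per arm, the chance that at least one arm has no events is 1 − (1 − 0.90^20)² = 1 − (1 − 0.122)² = 23%. That is not usual, an exact or likelihood-ratio test remains available, and redefining the endpoint would not remove the problem: at a 5% rate one arm is empty with probability 0.95^20 = 36%. An exact or penalised analysis is optional.
- **The word successful might have been meant as completion on treatment.** The protocol does not say so. If that was the intention, one sentence settles it.

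These replies narrow the point and lower its weight. They do not answer the classification in part 1 of the working. Because the protocol itself fixes the definition, this is not a detail left to an analysis plan.

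**Conclusion.** The point holds in limited form. As written, tolerability is a retention measure. It under-counts intolerance among participants who stop or step down but attend visit 4, and it over-counts it among those lost for unrelated reasons. If retention and unrelated loss are equal in the two arms, the between-dose difference shrinks by the factor (1 − u)(1 − s): to half if half of the intolerant participants stay and there is no unrelated loss, and to a fifth if 80% stay. The formula follows from the definition. The intolerance, retention and loss rates are assumptions, so the power figures are illustrations only.

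This should be corrected. It concerns a secondary endpoint in a signal-finding study, leaves the primary analysis untouched, and has partial back-up in the adverse-event and adherence data.

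**What to change.** 1. Define tolerability as remaining on the allocated dose to week 12, with no discontinuation and no step-down because of an adverse event.
2. Report study completion separately, by arm, as retention.
3. State how losses unrelated to treatment, and stops at the participant's request without an adverse event, are counted. One option is to treat them as missing and show the result with all counted as tolerant and all counted as intolerant.
4. State that the adherence denominator is capsules due at the allocated dose.
5. Reconcile the Dosage regimen text, which keeps the starting dose for the full 12 weeks, with the step-down option under Test drug dispensing. This is a matter of consistency, and the tolerability definition needs no change to any dosing rule.

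An exact or penalised comparison for sparse events may be added but is not required.

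The cost is wording. Adverse events with the action taken, dose changes and capsule counts are already recorded. The tolerability percentages may come out lower than completion percentages, by as much as stops and step-downs for adverse events occur among completers.
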